3. BACKGROUND, RATIONALE, AND OBJECTIVE

[figure not shown]
a. Background

To achieve global goals for the treatment of HIV, most high-prevalence countries are experimenting with and scaling up differentiated service delivery models (DSD). To date most of these efforts have focused on "stable" antiretroviral therapy (ART) patients, who have passed the period of high mortality and loss-to-follow-up immediately after initiating ART. Stable patients are believed to require fewer provider resources (e.g. clinical consultations) and are able to benefit from community-based service delivery that is closer to home[1] and from less intensive clinic visits. A handful of efforts have been formally described and evaluated in the literature[2–6]; many others are being implemented formally or informally under routine care, without a research or evaluation goal. While there is currently no reliable count of how many ART patients are participating in alternative service delivery approaches, it is likely that nearly every major HIV treatment partner supported by PEPFAR and the Global Fund have introduced one or more alternative models of care into the programs they support.

At present, some studies have reported outcomes for specific models of care and/or compared one model to another, and several large studies are currently underway to evaluate individual models. For most countries, though, we have little evidence on overall impact. We cannot currently estimate basic aggregate descriptive measures such as the proportion of clinics offering alternative models, the proportion of patients considered eligible or the number of patients actually participating. Nor do we know eligibility criteria for each model in each country, empirical resource utilization compared to traditional care, or core outcomes such as viral suppression. We have almost no data on variations among the models, duration of patient participation, fidelity to model guidelines, effects on clinic efficiency, and sustainability without external donor support. Many efforts are underway to improve use of alternative models, but their focus is on implementation rather than high-level evaluation or analysis of the phenomenon as a whole.

For purposes of this protocol, we will refer to any approach to service delivery that is tailored to some aspect of patient needs as a "differentiated service delivery model," or DSD. The original model of clinic-

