- Date ART initiated (first dose of medications dispensed)
- First-line regimen prescribed
- Any changes to first line regimens and dates of changes
- Dates, quantity (duration), and type for all medication collections
- Dates and results of all viral load tests
- Dates and results of all other laboratory investigations

DSD information

- Model(s) of care enrolled in and duration of enrollment
- Eligibility criteria and dates for alternative model of care
- Dates of participation in DSD activities (e.g. adherence club attendance, CCMDD pickups, multimonth dispensing, etc.)
- Other resources used for ART and recorded in the data source

In addition, we will collect aggregate, clinic- or DSD-level information about resources utilized, providers accessed, volumes served, etc. **This will not be human subjects research.** We will obtain this information from descriptions included in papers and reports, and, where necessary, surveys conducted by the study team.

c. Data Entry and Storage

The data sets that will be analyzed in this study will be shared with the study team by the Ministry of Health, implementing partners, or other researchers/evaluators. For all patient data extracted from paper files and registers, we anticipate entering all data onto electronic case report forms on tablets on site, so that paper forms do not need to be removed from the study clinics. Once patient information is captured on the tablet, the information will be immediately sent to a highly secure cloud server and wiped from the tablet. Once the databases are received by the study team, the data will be downloaded onto secure, protected drives at the HE²RO office in South Africa and at Boston University, with access limited to relevant study staff. Details on data transfer and drive security are provided under Subject Confidentiality below.

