7. DATA ANALYSIS

a. Sample Size

In order to measure national coverage of DSD, we will access data for up to the entire national ART cohort. In Malawi, the estimated number of individuals on ART is currently 740,000 [16]. This is expected to increase to \geq 90% of the entire HIV-infected population by the time the study ends. We therefore expect to collect and analyze data for up to 1,000,000 individuals, the estimated HIV-positive population in Malawi [16]. As noted above, all data will be drawn from records that exist at the time of data collection; the study will have no interaction with study subjects.

b. Outcomes

To estimate uptake, benefits, and costs of DSD, we will aim to report the following results, stratified by model care and/or other patient or clinic/model characteristics:

- Percentage of current ART patients eligible for any alternative model, under current guidelines
- 2. Demographic, economic, and clinical characteristics of patients in each model, as data allow.
- 3. Patient-months enrolled in any DSD and in each model
- 4. Frequency of transfer between models of care, including back to the conventional model
- 5. Location, duration, and frequency of ARV dispensing
- 6. Number of clinical visits/patient/year
- 7. Quantities of resources used/patient/year
- 8. Geographic distribution of patients enrolled in each DSD
- 9. Retention on ART, measured at 6-month intervals
- 10. Proportion virally suppressed (< 400 copies/ml³)
- 11. Other outcomes relevant to DSD that can be estimated from available data

Note: as this is not a clinical trial, we have not designated primary and secondary outcomes. We will report as many of the above outcomes as data allow.

c. Analysis

To evaluate the broad, national- or system-wide implications of differentiated models of ART delivery in the context of health systems in sub-Saharan Africa, we will conduct the following analyses.

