Outcomes 9-11 measure health outcomes by model of care. For these outcomes, we will begin with descriptive analyses of the characteristics of the population stratified by model of care. For each outcome described above, we will conduct a crude analysis comparing the proportion of subjects with the outcome by model of care. Next, we will conduct an analysis for each outcome accounting only for clustering using generalized estimating equations (GEE) with an unstructured correlation matrix and clustering by treatment site. In all cases the outcomes are dichotomous and therefore we will calculate risk differences comparing the intervention to the comparison arms using a linear link function and a binomial distribution. Next, should any imbalances between models of care be detected, we will adjust for those covariates in our GEE model. Finally, we will look for differences in the effects of the models of care by important baseline characteristics (e.g. size of the treatment population, rural vs. urban, province, etc.) using stratified analyses.

d. Dissemination of Findings

The results of this study will be disseminated as widely as possible in the study countries and globally. A full report will be made to local stakeholders and will be circulated widely and posted on our website. We will also develop a short briefing document to send to the Ministry of Health, donor agencies, and other interested organizations, and we will present the results at relevant conferences domestically and internationally. One or more journal manuscripts will be submitted to an appropriate peer-reviewed international journal.

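### Retention and suppression are compared by model of care with no common time zero, no rule for labelling patients who change model, and no restriction of comparators to eligible patients in care

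*Protocol*

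**What the plan says.** Protocol section 7c covers Outcomes 9–11 (retention, suppression, other outcomes) in steps. First, "we will conduct a crude analysis comparing the proportion of subjects with the outcome by model of care". Next, a GEE clustered by treatment site, in which "we will calculate risk differences comparing the intervention to the comparison arms using a linear link function and a binomial distribution". Then, "should any imbalances between models of care be detected, we will adjust for those covariates in our GEE model". The section does not say whether a patient's model is the first, the current, any ever used, or the one held at a given date.

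Section 7b lists "Retention on ART, measured at 6-month intervals" without saying from when. It defines suppression by a 400 copies/ml threshold without a measurement window. It also lists "Frequency of transfer between models of care, including back to the conventional model" as an outcome, so changes of model are expected, but section 7c does not say how the health-outcome comparison handles them.

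Other sections describe who enters DSD:

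- Section 3a says most efforts have focused on stable patients, "who have passed the period of high mortality and loss-to-follow-up immediately after initiating ART".
- Section 3b says most entrants to date were already suppressed.
- Section 3a adds that the conventional model may serve patients needing additional services.
- Section 5b admits everyone aged 15 or over in care from January 2014 to February 2021, with no exclusions.
- Section 6a dates large-scale DSD to 2015 or 2016.

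Section 6b collects "Model(s) of care enrolled in and duration of enrollment", eligibility dates, ART start and visit dates. Section 7c does not use them to set a time zero.

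**The concern.** A proportion of subjects by model needs one label per subject and one clock. If either depends on what happens during follow-up, the label carries information about the outcome. Three readings come to mind:

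- **Ever versus never in DSD.** A patient must still be in care to enter DSD. The time before entry is guaranteed retention credited to DSD, and everyone lost early falls into the never group (immortal time).
- **Model at the time of measurement.** If patients are returned to conventional care because of viraemia or missed visits, their failures count against conventional care (reverse causation).
- **DSD timed from DSD entry, conventional care from ART start.** This compares survivors of the early loss period with new starters.

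Adjusting for imbalanced covariates does not reallocate person-time or undo a label assigned after the outcome process began. With up to 1,000,000 records (section 7a), sampling error would be small and confidence intervals would give no warning. Section 3b expects little room for short-term improvement in health outcomes and intends the results to guide scale-up decisions, so a spurious gain of several points could decide the reading.

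**Working it through.** The protocol gives no attrition, uptake, viraemia or transfer rates and no effect size, so there is no stated figure to reproduce. All inputs below are assumptions, and the true effect of DSD is set to zero throughout.

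**1. Ever versus never, retention 12 months after ART start.** The annual attrition hazard is h1 for the first 6 months and h2 afterwards. DSD entry is possible only after 6 months, at rate λ per year among those in care. DSD status is ascertained up to H years.

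- In care at 6 months: S6 = exp(−0.5·h1). At 12 months: S12 = S6·exp(−0.5·h2).
- Ever in DSD by H: E = S6·[λ/(λ+h2)]·[1 − exp(−(λ+h2)(H−0.5))].
- Ever in DSD and retained at 12 months: R = S12·{1 − exp(−0.5λ) + exp(−0.5λ)·[λ/(λ+h2)]·[1 − exp(−(λ+h2)(H−1))]}.
- Risk difference = R/E − (S12 − R)/(1 − E).

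Example with h1 = 0.15, h2 = 0.05, λ = 0.5, H = 1: S12 = 0.9048, E = 0.2028, R = 0.2001. The ever group has 0.2001/0.2028 = 98.7% retained. The never group has (0.9048 − 0.2001)/(1 − 0.2028) = 88.4%. The difference is 10.3 points.

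| h1 / h2 | λ | H = 1 year | H = 2 years | H = 5 years |
|---|---|---|---|---|
| 0.15 / 0.05 | 0.5 | 10.3 | 17.0 | 40.3 |
| 0.15 / 0.05 | 1.0 | 12.8 | 29.5 | 72.1 |
| 0.25 / 0.06 | 0.5 | 15.9 | 24.8 | 50.6 |
| 0.25 / 0.06 | 1.0 | 19.4 | 40.1 | 78.4 |

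Simulation of the same set-up agrees to about 0.1 point. At H = 5 the never group is only 12–28% of patients and consists largely of early leavers, which is why the difference is so large.

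A different set of assumptions (entry 6–12 or 12–18 months after ART start, uptake 30% or 60%) gives these differences in 24-month retention:

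- attrition 15% in year 1 and 5% in year 2: 14–31 points;
- attrition 25% and 8%: 22–44 points;
- attrition 10% in both years: 9–24 points.

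**2. Landmark.** Take patients in care at 12 months and label them by model on that date. Under the null both groups then face the same hazard h2, so the next 12 months' retention is exp(−0.05) = 95.1% or exp(−0.06) = 94.2% in both, and the difference is 0.

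**3. Mismatched clocks.** With the second set of assumptions, 12-month retention from DSD entry minus 12-month retention from ART start is 7–10 points (15%/5%), 12–17 points (25%/8%) and 0 when attrition is constant (10%/10%).

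**4. Current model, suppression.** Viraemia v is equal in both groups, s is the share in DSD, and a fraction q of viraemic DSD patients is returned.

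- Viraemic among current DSD: v(1−q)/(1−vq).
- Viraemic among current conventional: [(1−s)v + svq]/[(1−s) + svq].
- The spurious suppression difference is the second minus the first.

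Results:

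- v = 0.05, s = 0.3, q = 0.3: 0.0395/0.7045 − 0.035/0.985 = 5.6% − 3.6% = 2.1 points.
- v = 0.10, s = 0.5, q = 0.6: 0.080/0.530 − 0.040/0.940 = 15.1% − 4.3% = 10.8 points.
- q = 0.1 with the same two pairs of v and s: 0.7 and 1.8 points.
- q = 0: 0.

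**The case against.** The strongest reply is that the protocol is silent rather than wrong. It never says that model of care is a fixed attribute, and index dates and exposure rules are often left to an analysis plan, which is not shown here. The fields collected would support a sound design, section 7c mentions baseline characteristics (though its examples are mostly site-level), and nothing prohibits a landmark analysis. Outcomes 9 and 10 are two of ten named outcomes (the eleventh is open-ended), none of them primary, in a record review.

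Much of this stands as a limit on wording. A reader might infer that the plan has bias built in. The text does not support that, because which bias arises depends on a label the protocol does not define. A reader might also infer that patients are sent back because of viraemia or missed visits. The protocol counts transfers but gives no reasons for them, so that mechanism is conditional.

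It does not remove the point. The protocol already fixes the population, the subject-level comparison and the order of models, and it describes the selection into DSD that makes the obvious readings fail. The later GEE steps state no different label or clock.

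**Conclusion.** The concern holds as a failure to define time zero, the model label and the eligible comparator for Outcomes 9–11. As written, the retention and suppression contrasts cannot be interpreted as effects of the models, and the likely errors mostly favour DSD.

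The size depends on the reading. For ever/never labels it is about 10–19, 17–40 or 40–78 points of 12-month retention with 1, 2 or 5 years of ascertainment. For current-model labels it is about 1–2 points of suppression if 10% of viraemic DSD patients are returned, 2–11 if 30–60% are, and 0 if none are. For mismatched clocks it is 0–17 points.

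These figures are illustrative and rest on the assumed rates. The 40–78 range should not be quoted without its 5-year ascertainment. Nor should the mechanisms be added together, since they arise under different labelling rules. The zero under a landmark assumes that uptake among those still in care is unrelated to prognosis, so a common time zero does not remove ordinary confounding.

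**What to change.** Amend section 7c for Outcomes 9–11, before these outcomes are analysed, to state:

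- **Time zero.** For DSD patients, the DSD enrolment date. For comparators, a date on which they were eligible, in care and still in the conventional model, matched on time on ART and calendar period (sequential or landmark cohorts).
- **Label.** The model at time zero, kept after any later transfer.
- **Windows.** 6-month retention intervals and the viral load window both counted from time zero.
- **Adjustment.** Keep covariate adjustment, for residual confounding by prognosis.
- **Sensitivity.** An analysis with model of care as a time-varying exposure.

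The cost is wording and programming, since the required dates are already in the section 6b field list. The main downside is that patients without a dated enrolment or eligibility drop out of this contrast. That matters because section 6a says the national electronic system does not fully capture model of care, so the number lost should be reported. Keeping the label after transfer also means that comparators who later enter DSD dilute the contrast; the time-varying analysis helps to show how much.

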5. STUDY SITES AND POPULATION

a. Study Sites

The evaluation will be conducted nationally in Malawi. Data collected may pertain to the entire national cohort of ART patients (e.g. Baobab Health NART) or to specific smaller cohorts developed by implementing partners, other researchers, and clinics themselves.

b. Inclusion Criteria

This study aims to measure coverage and outcomes of DSD across Malawi. For this reason, we will include in our study all adults who are accessing care for HIV anywhere in the country. The inclusion criteria are shown below.

Inclusion criteria

- ≥ 15 years old
- Patients accessing care for HIV within the data collection period (January 1, 2014 to February 28, 2021)
- In any HIV transmission risk group (general adults and adolescents, high transmission risk populations)

Exclusion criteria

None

Children younger than 15 are excluded from this study for two reasons. First, they are typically treated in pediatric HIV programs that have different drug regimens, visit schedules, and models of care than do adults. Second, the vast majority of DSD implementation in the focus countries to date has involved only adult and adolescent patients, not children [15].

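### The GEE for retention and viral suppression pairs an unstructured correlation matrix with treatment site as the cluster, so its correlations have no meaning and its estimates depend on the order of patients in the file

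*Protocol*

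**What the plan says.** Protocol section 7c deals with outcomes 9-11 (retention, viral suppression, and other outcomes the data allow) in steps. A crude comparison by model of care comes first. Next is an analysis "accounting only for clustering using generalized estimating equations (GEE) with an unstructured correlation matrix and clustering by treatment site". The same paragraph says the team will "calculate risk differences comparing the intervention to the comparison arms using a linear link function and a binomial distribution". If models of care are found to be imbalanced, covariates are added to this same GEE, and stratified analyses follow.

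The treatment site is the only cluster named. No other correlation structure is offered, as an alternative or as a fallback.

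On scale, section 7a states that "the estimated number of individuals on ART is currently 740,000" and adds: "We therefore expect to collect and analyze data for up to 1,000,000 individuals". Section 5a says: "Data collected may pertain to the entire national cohort of ART patients". It also allows smaller cohorts. The number of sites and the number of patients per site are not given. Section 7b lists outcome 9 as "Retention on ART, measured at 6-month intervals".

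**The concern.** An unstructured working correlation suits a few measurements in a fixed order, such as visits 1 to 4 of each patient. The correlation between positions 1 and 2 is then the same quantity in every cluster and can be pooled across clusters. With the clinic as cluster, position 1 is whichever patient the file lists first. The correlation between the first and second listed patients of one clinic has no counterpart in another clinic, so pooling it estimates nothing.

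At stake is the only analysis of the health outcomes that accounts for clustering, and the only one that adjusts for covariates. The adjusted model reuses the same GEE, so the fault carries into the adjusted risk differences. A result that changes when the data file is sorted differently cannot be reproduced by a second analyst.

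**Working it through.** The plan gives no figure of its own to reproduce here, because no power or precision calculation rests on this model.

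**Inputs.** N = 740,000 currently on ART and up to 1,000,000 to be analysed (section 7a). The cluster is the treatment site and the matrix is unstructured (section 7c). The number of sites K is not in the protocol, so the values below are assumptions.

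**Step 1: number of correlations.** With an average of m = N/K patients per site, an unstructured matrix has m(m − 1)/2 correlations.

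| N | Assumed K | m | m(m − 1)/2 | Correlations per site |
|---|---|---|---|---|
| 740,000 | 500 | 1,480 | 1,480 × 1,479 / 2 = 1,094,460 | 2,189 |
| 740,000 | 1,000 | 740 | 740 × 739 / 2 = 273,430 | 273 |
| 740,000 | 2,000 | 370 | 370 × 369 / 2 = 68,265 | 34 |
| 1,000,000 | 500 | 2,000 | 2,000 × 1,999 / 2 = 1,999,000 | 3,998 |
| 1,000,000 | 1,000 | 1,000 | 1,000 × 999 / 2 = 499,500 | 500 |

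Each site contributes at most one pair to each correlation. For 740,000 patients, the correlations would fall to the number of sites only at about 6,475 sites (m about 114).

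**Step 2: the estimated matrix.** Binary outcomes were simulated with an assumed prevalence of 0.85 and an assumed intra-site correlation of 0.05. The moment estimate of the unstructured matrix, with its diagonal fixed at 1, was then checked for positive definiteness.

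| Sites × patients per site | Non-positive eigenvalues |
|---|---|
| 30 × 10 | 0 |
| 30 × 40 | 8 |
| 100 × 50 | 1 |
| 100 × 200 | 50 |
| 300 × 400 | 62 |
| 500 × 1,000 | 252 |
| 700 × 1,400 | 351 |

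Only the smallest setting gave a usable matrix.

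**Step 3: the risk difference.** A binomial GEE with identity link was fitted to one simulated data set of 60 sites × 40 patients, with a true difference near 0.03. Between fits, only the order of patients within each site was changed.

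| Ordering | Unstructured: RD (SE) | Exchangeable: RD (SE) |
|---|---|---|
| 1 | 0.054 (0.007), not converged | 0.037 (0.015), converged |
| 2 | 0.052 (0.008), not converged | 0.037 (0.015), converged |
| 3 | 0.032 (0.008), not converged | 0.037 (0.015), converged |

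The unstructured standard error is about half the exchangeable one (0.007/0.015 = 0.47; 0.008/0.015 = 0.53). It is too small even for the variation that sorting creates: the estimates differ by 0.054 − 0.032 = 0.022, which is 0.022/0.008 = 2.75 of the reported standard errors, with the same data.

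A separate simulation of the same size gave the same picture: reordering moved the unstructured estimate from −0.009 to 0.038, while the exchangeable and independence fits did not move. With 60 sites × 80 patients, the unstructured fit gave −0.041 without converging, against 0.032 (exchangeable) and 0.029 (independence).

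**The case against.** The strongest defence is that a working correlation is a nuisance choice. GEE estimates stay consistent when it is wrong, provided that robust standard errors are used, and software usually adjusts a matrix that is not positive definite and returns a result. This holds for a structure with few parameters. It does not help when the matrix has thousands of entries fitted to the same residuals, as the movement under reordering shows.

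A second defence is that the unstructured matrix was meant for the 6-monthly retention measurements within a patient. It would be workable there, but section 7c makes the site the cluster, and viral suppression has no stated repeat schedule.

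Third, site sizes are not stated, and section 5a allows smaller cohorts. Section 6b also notes that viral loads will be missing for patients newly starting treatment. So the counts above are illustrative upper-scale figures for a national data set. This stands. In a small cohort with about ten patients per site the matrix may be computable, but its entries would still follow an arbitrary order.

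Three stronger readings are tempting and not supported:

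- A reader might infer that the matrix is singular whenever sites hold more patients than there are sites, that is, below about 860 sites (the square root of 740,000). With the diagonal fixed at 1, that rank limit does not apply. At 500 × 1,000 it would require at least 500 zero eigenvalues; there were 252 non-positive ones, and the matrix was of full rank but indefinite. It also failed at 100 × 50, on the supposedly safe side, so 860 is no boundary.
- A reader might infer that the analysis cannot run. Software may return an answer; the trouble is that the answer is unreliable.
- A reader might infer that "using a linear link function and a binomial distribution" is also an error. It is a standard direct route to the risk difference the plan wants. Convergence trouble is possible once covariates are added, but the protocol's remark in section 3b that most alternative-model patients were suppressed at entry does not establish it, and a fallback is ordinary SAP content.

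Finally, the protocol names no primary outcome and also plans crude and stratified comparisons, so not every result on outcomes 9-11 depends on this model. That limits the reach of the fault but does not remove it.

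**Conclusion.** The specification is wrong as written and needs correcting. The core of the point needs no assumption: with the site as cluster, pairwise correlations between patient positions have no meaning at any sample size. The counts of 273,430 to 1,094,460 correlations rest on 500 to 1,000 assumed sites and on all 740,000 patients contributing. Over assumed site numbers from 50 to 2,000, correlations exceed sites at least 34-fold. The halved standard errors and the order-dependent estimates come from simulations at one assumed prevalence and intra-site correlation, with far fewer patients than the study expects. They show the direction and kind of harm, not its exact size in the Malawi data. Because the protocol states this choice outright, it is not a detail left open for a SAP.

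**What to change.** In section 7c, replace the unstructured correlation matrix with: *independence working correlation (exchangeable as a sensitivity analysis) with robust sandwich standard errors clustered by treatment site*. State that this applies to both the unadjusted and the covariate-adjusted GEE.

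Independence has no correlation parameters and exchangeable has one, whatever the site size, and neither depends on patient order. Clustering the robust standard errors by site also allows for repeated 6-monthly records of patients who stay at one site. The risk difference and the link can stay as planned.

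The cost is one sentence of protocol wording. No data, sample or outcome definition changes.
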